1.0 SUMMARY of INVESTIGATION

Study Title:	Prospective, Parallel, Multicenter Randomized Controlled Study Investigating the Effects of UVC Beam and Laser Beam Therapy According to Standard Therapy in Patients with Covid-19 Diagnosis
Study Code:	MD2020/001
Device :	Turkishbeam Model Number: 1007-001
	*: The device was produced by RD GLOBAL ARASTIRMA GELISTIRME SAĞLIK ILAÇ INSAAT YATIRIMLARI A.S.
Device Classification:	Class III
Purpose of the Study:	Clinical research study that evaluates the effect of Turkish Beam- Selective UV developed by RD GLOBAL ARASTIRMA GELISTIRME SAĞLIK ILAÇ INSAAT YATIRIMLARI A.S. use into Intravascular, Intrapulmonary, Intratracial, Intrarespiratory area. Bacteria, Fungal and Virus-based pathogens systematically to collect and evaluate specific clinical performance and safety data. In our Clinical Research, we aimed to investigate the effectiveness of the treatment group and control group mortality rates, intensive care hospitalization times, monitoring the virus load by PCR, and the treatment effectiveness of UVC

Scope of the Study:	This Clinical Research covers determining the treatment effectiveness and reliability of UVC application to patient groups, the details of which are determined in the protocol.
Application:	Intravascular, Intrapulmonary, Intratracial, Intrarespiratory UVC and Laser Therapy System
Overall Study Design:	Prospective, Parellel, Multicenter, Randomized Controlled
Number of volunteers:	50 patient- 2 groups with 25 (two hundred) patients in each group
Treatment Groups:	Test: Antiviral + Antimalarial + Antibiotic Treatment + UVC Therapy Control: Antiviral + Antimalarial + Antibiotic Treatment
Groups of Volunteer:	Those who are between the ages of 40-75 and who have applied to the clinic with symptoms such as fever, weakness, cough, and shortness of breath, or who have signs of COVID-19 (SARS- CoV-2) test positive or atypical pneumonia findings in CT findings and accepted as COVID 19 infection, and patients undergoing intubation treatment in intensive care unit
Sensitive population / Vulnerable subjects:	The study will not include under-40, pregnant women and those with suspected pregnancy, previously diagnosed with mental disorders, puerperant women and lactating women

Duration of the clinical trial: 3 months (04.2020- 07.2020)

Researched Medical Condition:

and Disease

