5.6 Secondary Endpoints

- Hypersensitivity
- Temporary shortness of breath
- Rarely, redness of the skin is due to heat
- Edema
- Bleeding
- Embolization
- Hematoma
- Hyperpigmentation
- Ache
- paresthesia
- Superficial thrombophlebitis
- May cause urticaria or ulcers.
- Vascular rupture and perforation
- Visible scratch
- Iatrogenic injury may damage the surrounding tissues.
- Hemothorax or pneumothorax.
- Neighboring Nerve Damage Iatrogenically
- phlebitis
- Skin Burn or discoloration

If two or more adverse effects from the above adverse effects are seen, the study is terminated.

6. Statistical Evaluation:

- According to the course of the clinical trial, if we reach the research arm (100 patients), control group (100 patients), the efficacy and safety of the treatment will be examined and an interim report will be prepared. According to the results of the interim report, the clinical trial will be terminated or the clinical trial will be continued until the number of volunteers (400 in total) mentioned above is completed.
- In this interim analysis, the patients completing the study will be evaluated considering the primary and secondary endpoints stated in the protocol and the criteria are as follows:

1-Duration in intensive care

2-Survival rate

Contribution of UVC and laser beam application to the treatment of 3-COVID 19 infection and / or superinfections accompanying COVID 19 infection

The tests to be applied are as follows:

1-Difference test between two averages for intensive care stay

(Mann-Whitney U test or t test) will be used.

2-Survival analysis tests will be used for survival rate.

Accompanying 3-COVID 19 infection treatment and / or COVID 19 infection

To investigate the contribution of UVC and laser beam application to the treatment of superinfections

Chi-square test will be applied.

Descriptive statistics will also be given for demographic data.

REFERENCE STUDIES ABOUT THE APPLICATION OF UVC BEAM "in vitro, in vivo and ex vivo"

1. The Effect of UV-C Ray Reducing Pathogen Rate on Blood Platelets Apps;

Auto-immune diseases HIV 1 -2
T-lymphotropic virus types 1 and 2
Hepatitis B (HBV)
Hepatitis C (HCV)
Hepatitis A and E
Blood pathogens (Treponema pallidum)
Parvovirus B19

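### Section 6 lets an interim report end the trial with no significance level, stopping boundary or order among three criteria, so type I error is uncontrolled

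*Combined protocol and SAP*

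**What the plan says.** Section 6 (Statistical Evaluation) makes the interim conditional on recruitment: "if we reach the research arm (100 patients), control group (100 patients), the efficacy and safety of the treatment will be examined". What follows is a decision: "According to the results of the interim report, the clinical trial will be terminated or the clinical trial will be continued", in the second case "until the number of volunteers (400 in total) mentioned above is completed".

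On content, Section 6 says that "the patients completing the study will be evaluated considering the primary and secondary endpoints stated in the protocol and the criteria are as follows". Three criteria follow: duration in intensive care, survival rate, and the contribution of UVC and laser application to treating COVID-19 and/or accompanying superinfection. A sentence beginning "The tests to be applied are as follows" then assigns a t test or Mann-Whitney test to the first, unnamed survival analysis tests to the second and a chi-square test to the third.

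The document gives no significance level, sidedness, stopping boundary, multiplicity rule or ranking of the three criteria. It does not say whether one, some or all must succeed. It describes no separate final analysis. Section 5.5 defines the primary endpoint as death, or else a set of recovery items all being met, and Section 6 does not say how its three criteria relate to that endpoint.

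The Section 1.0 summary gives a different size: "50 patient- 2 groups with 25 (two hundred) patients in each group".

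**The concern.** An interim look at efficacy that can end a trial is a second opportunity to claim success. Several unranked criteria multiply those opportunities. Each needs a threshold fixed in advance, or a nominal p value no longer tells the reader how often such a result would arise by chance.

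Here both features are present and neither is controlled. With results in hand at 200 patients, the sponsor could stop on whichever criterion looked favourable, or continue and analyse again. The plan could not show afterwards that this choice was made independently of the data. The trial tests a Class III device in intubated patients, and Section 4.8 already predicts a significant increase in survival, so a positive conclusion should carry a known error rate.

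**Working it through.** The plan states no alpha, power or sample-size derivation, so there is no figure of its own to reproduce. The calculation shows how large the problem is under stated assumptions.

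**Inputs from the document.** Interim at 100 + 100 = 200 patients, maximum 400, three criteria with separate tests (all Section 6). Information fraction by patient count: 200/400 = 0.50.

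**Assumptions, none of them in the document.** Each test is two-sided at 0.05 (critical value 1.96). A positive result on any one criterion suffices. The same tests are repeated at 400. The information fraction is one half. The correlation between criteria is 0 to 0.95.

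1. *One criterion, two looks.* The interim and final statistics have correlation √0.5 = 0.707. P(|Z1| > 1.96 or |Z2| > 1.96) = 0.0831, or **8.3%**.

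2. *Three independent criteria, one look.* 1 − 0.95³ = 0.143, or **14.3%**.

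3. *Three independent criteria, two looks.* 1 − (1 − 0.0831)³ = 0.229, or **22.9%**.

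4. *Correlated criteria and other decision rules,* by simulation of equicorrelated normal statistics (2,000,000 replicates):

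| Correlation | Any of three, one look | Any of three, two looks | Any of three, two looks, favouring UVC only | All three required, two looks |
|---|---|---|---|---|
| 0 | 14.3% | 22.9% | 12.0% | 0.02% |
| 0.3 | 13.6% | 21.9% | 11.1% | 0.2% |
| 0.5 | 12.6% | 20.2% | 10.2% | 0.6% |
| 0.8 | 9.8% | 15.9% | 7.9% | 2.5% |
| 0.95 | 7.4% | 12.0% | 6.0% | 5.1% |

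   The UVC-only column is to be compared with a nominal 2.5%.

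5. *Other per-test levels* (any of three, two looks). At 0.01: 5.2% if independent, 4.8% at correlation 0.5. At 0.10: 40.8% and 36.1%.

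6. *Check of a remedy.* For one criterion with half the information at the interim, the classical O'Brien-Fleming limits are |Z| > 2.797 and |Z| > 1.977, that is p < 0.0052 and p < 0.0480. The overall error is 5.0%. With an effect that gives a single 0.05 test 80.0% power (drift 1.960 + 0.842 = 2.802), the two-look design has 79.7%.

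7. *If the trial has 50 patients.* A look at 200 cannot occur. Only the one-look column applies: about 7% to 14%.

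**The case against.** A reader might infer that the trial's false-positive rate is in fact well above 5%. The documents do not support that as a statement of fact. They give no per-test level and no rule for combining the criteria, and other readings lead elsewhere. If all three criteria had to be significant, the rate would be 0.02% to 5.1%. At 0.01 per test with any one sufficing, it would be about 5%. If termination were only for futility or harm, the interim would add no false efficacy claims. Calling the tests unadjusted is also too strong, because the document is silent on adjustment.

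A reader might also infer that each criterion is explicitly planned for testing at 200 and again at 400. Section 6 introduces the criteria as those of the interim analysis, and the list of tests follows. Repetition at 400 is a reasonable inference, since continuing has little purpose without a further analysis and no other tests are given, but it remains an inference.

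The upper figure of 22.9% requires independence, which is unlikely for ICU stay, survival and infection outcome in the same patients. The two-sided figures also count results favouring control. Finally, the interim is conditional, and at the summary's 50 patients it cannot happen.

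All of this stands against a definite rate. It does not answer the gap itself. Section 6 says that efficacy is examined and that the results decide termination, so stopping for benefit is open. Each milder reading needs a rule that the plan does not contain. Settling the sample size does not close the gap either: at 50 patients three unranked tests remain.

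**Conclusion.** The concern holds as an absence of control. An interim that examines efficacy and safety can end the trial on three separately tested criteria, with no alpha, boundary, order, success rule or stated direction of termination. The type I error is undefined, so a positive claim would carry no known error rate.

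The range of about 12% to 23% is an illustration. It rests on 0.05 two-sided per test, any one criterion sufficing, the same tests at 200 and 400, half the information at the interim, and correlations from 0.95 down to 0. On the same per-test level, one criterion tested twice gives 8.3%, and three criteria at a single look give about 7% to 14%. None of these should be quoted as the trial's actual error rate. The gap needs closing before any comparative data are seen, because a rule written afterwards cannot restore the error rate.

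**What to change.** 1. Reconcile the 50 patients of Section 1.0 with the 400 of Section 6. Whether an interim exists depends on this.
2. State an overall two-sided alpha of 0.05. Name one primary criterion, with one named test, consistent with Section 5.5, as the only criterion that can support an efficacy stop. Survival is a natural choice, since death is the first element of the Section 5.5 endpoint; another single criterion would fit the same structure.
3. If the interim is kept, say whether termination may be for benefit, futility or harm. For benefit, use an O'Brien-Fleming-type alpha-spending boundary evaluated at the actual information fraction. For survival, that fraction is the number of deaths observed relative to the number planned, which need not be one half at 200 of 400 patients. At exactly one half, the classical limits are about p < 0.005 at the interim and p < 0.048 at the end.
4. Test the remaining criteria in a fixed, stated order, only after the primary is significant.
5. If 50 is the real size, delete the interim and keep the single primary criterion and the fixed order.

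The cost is a short rewrite of Section 6 and a final threshold near 0.048 instead of 0.05, with negligible power loss (80.0% to 79.7% in the example above). ICU stay and treatment contribution could be claimed only if the primary criterion succeeds.

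### Section 6 promises a safety evaluation of the secondary endpoints, but none of the 19 adverse effects in 5.6 enters its criteria or tests, and it evaluates completers only

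*Combined protocol and SAP*

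**What the plan says.** Section 1.0 makes safety a purpose of the study: "to collect and evaluate specific clinical performance and safety data". Section 6 repeats this for the interim, where "the efficacy and safety of the treatment will be examined and an interim report will be prepared". The consequence follows: "According to the results of the interim report, the clinical trial will be terminated or the clinical trial will be continued". The evaluation is to be made on patients who complete the study, "considering the primary and secondary endpoints stated in the protocol and the criteria are as follows".

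Three criteria follow: "1-Duration in intensive care", "2-Survival rate", and the contribution of the beam treatment to treating COVID-19 and/or "superinfections accompanying COVID 19 infection". Each has its own method: a Mann-Whitney or t test for intensive care stay, survival analysis for survival, and a chi-square test for the infection criterion. Descriptive statistics are promised for demographic data only.

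Section 5.6 defines the secondary endpoints as a list of adverse effects, among them bleeding, embolization, vascular rupture, hemothorax or pneumothorax, and skin burn. Below the list stands a rule that the study ends if two or more of these effects are seen. The follow-up programme in Section 5.4 records adverse events from inclusion on Day 0 to the follow-up visits on Days 7 and 15.

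**The concern.** The endpoints Section 6 says it evaluates and the criteria it then lists do not match. Followed as written, the plan collects the 5.6 effects at every visit from inclusion onwards. It gives no per-arm count, comparison or interval for them, at the interim or later, because there is no other analysis section.

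This matters because safety is a declared purpose and a declared part of a stop-or-continue decision. Section 4.8 already concludes that the risk is minimal and that the device adds none, and the plan contains no analysis of the 5.6 effects that could test this. Several listed effects can also come from the illness. Temporary shortness of breath is in 5.6 while dyspnea is in the inclusion list of 5.2. Bleeding and hematoma are in 5.6 while thrombocytopenia is in 5.2. For such items only the control arm can separate device effects from disease.

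The restriction to completers makes the gap worse. On its plain reading, a patient who left early because of a listed effect would not be in the evaluated set.

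**Working it through.** The plan states no adverse-event rate, alpha, power or sample-size derivation, so it has no figure to reproduce. The main check is a comparison of text.

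**Section 5.6 against Section 6**

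| Section 6 criterion | Method | Where it belongs | Contains a 5.6 item? |
|---|---|---|---|
| Time in intensive care | Mann-Whitney or t test | in neither 5.5 nor 5.6 | No |
| Survival | survival analysis | death component of 5.5 | No |
| Contribution to treating infection or superinfection | chi-square | overlaps 5.5 at most | No |

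Of the 19 items in 5.6, none is in a criterion (0 of 3) or a test (0 of 3).

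**What a clean record would show.** For 0 events in n patients, the exact (Clopper-Pearson) two-sided 95% upper limit is 1 − 0.025^(1/n).

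- n = 100 (interim arm, Section 6): 1 − 0.025^(1/100) = 3.6%, about 1 in 28
- n = 200 (half of the 400 in Section 6): 1 − 0.025^(1/200) = 1.8%
- n = 25 (the numeral in Section 1.0): 1 − 0.025^(1/25) = 13.7%, about 1 in 7

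**Which size applies.** Section 1.0 gives 50 patients in total, with each group as 25 in figures and two hundred in words. 2 × 25 = 50 and 2 × 200 = 400; Section 6 gives 400. The interim needs 100 + 100 = 200 patients, which is half of 400 but four times 50. With 50 patients it cannot take place, so 3.6% is the limit at the interim and 13.7% concerns only a final report of a 50-patient study.

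**What the 5.6 rule supplies.** Suppose it counts affected patients across both arms (an assumption; the text does not say). With per-patient rate p, the chance of at least two among N patients is 1 − (1 − p)^N − Np(1 − p)^(N − 1).

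| Assumed p | N = 50 | N = 200 |
|---|---|---|
| 1% | 9% | 60% |
| 2% | 26% | 91% |
| 5% | 72% | nearly 100% |

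On this reading, a study that reaches the interim has had at most one affected patient, so the largest contrast available is 1/100 against 0/100.

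**Estimation or testing.** Illustrative power at two-sided 0.05 for assumed rates of 5% against 15% is 21% at 25 per arm, 66% at 100 and 92% at 200. For 10% against 5%, the 95% half-width of the risk difference is 1.96 × √(0.10 × 0.90/n + 0.05 × 0.95/n). This gives 14.5 points at 25, 7.3 at 100 and 5.1 at 200. Intervals are informative at all these sizes; a test at 25 per arm is not.

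**The case against.** A reader might infer that the plan yields no between-arm safety result at all. The documents do not support that. Survival is compared by arm, death is part of the primary endpoint in 5.5, and mortality in intensive care patients is safety evidence. What survival does not measure is non-fatal harm such as nerve damage or burns.

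A reader might also infer that adverse effects play no part in stopping. The 5.6 rule shows otherwise. It is a bare count, however, and produces no estimate for either arm. If it is study-wide, a between-arm contrast at the interim will be nearly empty. That weakens the comparison as a decision tool, but it makes the zero- or one-event case the expected one, and that is where upper limits are most needed.

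The sentence introducing the criteria can be read more mildly in this translated text: the endpoints, plus some further criteria. Safety would then be promised with its method left open. Saying that the effects will never be compared is therefore an inference from silence. Even on the mild reading, no method, denominator or table is given for 5.6, while descriptive statistics are specified for demographics.

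Some items, such as visible scratch, iatrogenic injury or skin burn, arise mainly from a procedure that controls do not receive. For these, description in the UVC arm is reasonable. The need for comparison is limited to the overall count and to items that controls can also have.

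Finally, the zero-event limits reflect sample size and would be the same under a complete plan. They show why intervals must be reported, not what the omission costs. This stands.

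**Conclusion.** The point holds in this form. Section 6 says it evaluates the secondary endpoints and safety, yet no 5.6 item is in any of its three criteria or tests. Apart from survival, the only use of adverse effects is a count rule without arm, unit or denominator. The completer restriction could remove patients harmed early. This is more than missing detail, because the listed criteria do not cover the endpoints they are said to represent. It should be corrected.

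A clean record at the interim would still be compatible with a true rate of up to 3.6% per arm for any one effect. The corresponding limit is 1.8% at 200 per arm and 13.7% at 25. It would be wrong to present 13.7% as the uncertainty at the interim, since the interim cannot occur at that size.

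The textual finding needs no assumption. The upper limits assume only independent patients and zero events. The count-rule and power figures rest on assumed rates and, for the former, on a study-wide count of affected patients.

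**What to change.** 1. **Add a safety criterion to Section 6**, and correct the sentence introducing the criteria so that it covers the 5.6 list. Suggested wording: *By arm, among all randomised patients who started their allocated treatment, the number and percentage with at least one Section 5.6 effect and with each effect, with exact 95% confidence intervals; the risk difference with its 95% confidence interval for the overall count and for effects that can also occur in control patients. These are estimates; no formal test is planned.* Name in advance which effects fall in the last group.
2. **Use that denominator for safety in place of completers only.**
3. **Report a zero count with its upper confidence limit**, and state that it will not be presented as proof of safety.
4. **Reconcile the 5.6 rule with the Section 6 stop-or-continue decision.** The documents must say what the rule counts, in which arm and over what denominator, and how the two provisions relate. Which rule should apply is for the sponsor and investigators to settle.
5. **Reconcile the sample sizes** in Section 1.0 (50; 25 and two hundred per group) and Section 6 (400, with an interim at 100 per arm), because they decide whether the interim exists.

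The safety analysis itself costs some plan wording and one table, as the Adverse Event row already collects the data. Items 4 and 5 need a sponsor decision and an amendment of the text. The safety statement will be less favourable than a bare report of few or no events.

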2.0 DESIGN of STUDY

2.1 DESIGN

Prospective, parallel, multicentre, randomized controlled study Ages between 40 and 75 years of age and positive symptoms such as fever, malaise, cough, and shortness of breath, or positive atypical pneumonia in CT findings or COVID-19 (SARS-CoV-2) test In the intensive care unit, which is accepted as COVID 19 infection and has been treated, patients will be treated with UVC radiation and laser beam treatment according to IKU principles in addition to Antimalarial therapy + Antiviral therapy + Antibiotic therapy. Standard

treatment consisting of Antimalarial therapy + Antiviral therapy + Antibiotic therapy will be applied to the control group. The dosage of the standard treatment consisting of antimalarial therapy + Antiviral therapy + Anitibiotic therapy, the number of days of treatment, and its active ingredient are indicated in the table.

Treatment in Possible / Definitive COVID 19 Cases with Pneumonia						
Oseltamivir** tb 75 mg	2x75 mg, oral	5 days 5 days				
Hydroxychloroquine, 200 mg tablet	Following 2x400 mg loading dose, 2x200 mg tablet orally	5 days				
According to the physician's d	ecision					
+\$	Day 1 500 mg, oral	5 days				
Azithromycin ***	4 days following 250 mg/day					
Severe cases that did not respo	ond to the first treatment					
Favipravir 200 mg tablet	2 x 1600 mg 2 x 600 mg	5-7 days				
Or						
Lopinavir 200 mg / ritonavir 50mg tablet	2 x 2 tablet, oral	10-14 days				

Source: COVID-19 (SARS-CoV2 INFECTION) GUIDE (Scientific Board Study) T. C. MINISTRY OF HEALTH 25 MARCH 2020

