5.0 METHODOLOGY

5.1 Patient Admission Criteria (Diagnosis / Medical Table)

Symptoms such as fever, weakness, cough, mild shortness of breath between the ages of 40-75 referring to the clinic with COVID-19 (SARS-CoV-2) test positive or atypical in CT findings. Patients with signs of pneumonia and considered COVID 19, undergoing intubation treatment in the intensive care unit, and meeting the inclusion / exclusion criteria. Patients who are not found suitable according to the intervals specified in the Inclusion / Exclusion criteria will not be included in the study.

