5.3 Exclusion Criteria

- Under 40 years old
- *Pregnant women and those with suspected pregnancy*
- Those with a history of anaphylaxis
- Those with known DNA repair deficiencies:
- Those diagnosed with mental disorder,
- puerperant women and lactating women

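### The starting point for counting ICU duration is not defined, although patients are described as already in the ICU and intubated at entry; counting from randomisation would be a cheap gain in precision

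*Combined protocol and SAP*

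**What the plan says.** **The outcome.** Section 6 (Statistical Evaluation) gives three criteria for the interim report, on whose results the trial is ended or continued. The first in the list is "1-Duration in intensive care". The matching test is described as "1-Difference test between two averages for intensive care stay", by Mann-Whitney U or t test. The statement of purpose in Section 1.0 names the same quantity as "intensive care hospitalization times". No section states a start, an end, or how a death is counted.

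**The patients.** Section 1.0 refers to "patients undergoing intubation treatment in intensive care unit". Section 5.1 admits patients "undergoing intubation treatment in the intensive care unit, and meeting the inclusion / exclusion criteria". Section 2.1 also places them in the ICU: "In the intensive care unit, which is accepted as COVID 19 infection and has been treated".

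**Limits and adjustment.** Neither the inclusion list (5.2) nor the exclusion list (5.3) caps the time already spent in the ICU. The exclusions concern age, pregnancy, puerperal or lactating women, anaphylaxis, mental disorder and "Those with known DNA repair deficiencies". Section 6 plans no adjustment for prior ICU days.

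**The schedule.** The treatment and follow-up table puts randomisation at Day 0 and the last visit at Day 15. It has a medical history row, but none for ICU admission, ICU discharge or ventilation status.

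**The concern.** A stay in intensive care ordinarily runs from admission to discharge. If patients are randomised part-way through that stay, the measured outcome is the sum of two parts: days before randomisation, which treatment cannot alter, and days after it, which treatment might alter. The first part adds spread without adding any treatment effect.

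An invented pair of patients shows the mechanism. One is randomised 12 days after ICU admission and leaves 5 days later, so the stay is 17 days. The other is randomised after 1 day and leaves 10 days later, so the stay is 11 days. The patient with the shorter course under treatment has the longer recorded stay.

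What is at stake is the sharpness of one of the criteria behind the decision to stop or continue. Because the trial is multicentre and the origin is unstated, centres or analysts could also count from different points.

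**Working it through.** **The plan's own figure.** Section 1.0 gives 50 patients (25 per group, with the words two hundred in brackets). Section 6 gives an interim at 100 per arm and 400 in total. No effect size, SD, alpha or power is stated, so none of these sizes can be reproduced. The conflict between them is a separate matter. Both 25 and 100 per arm are carried through below.

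**Assumptions, none of them from the documents.** The SD of ICU days after randomisation is 8. The SD of ICU days before it is 3 to 5. The correlation between the two parts is r, first set to 0.

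**1. Variance of the total stay relative to the post-randomisation part**

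Ratio = (8² + s² + 2·r·8·s) / 8², where s is the prior-day SD.

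| s | r | Ratio |
|---|---|---|
| 3 | 0 | (64 + 9)/64 = 1.14 |
| 5 | 0 | (64 + 25)/64 = 1.39 |
| 5 | -0.3 | (64 + 25 - 24)/64 = 1.02 |
| 5 | +0.3 | (64 + 25 + 24)/64 = 1.77 |

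At r = 0 the effective sample falls to 1/1.14 = 0.88 or 1/1.39 = 0.72, a loss of 12% to 28%. The inflation disappears when r = -s/(2·8), which is -0.19 for s = 3 and -0.31 for s = 5. The size therefore depends on a correlation that the documents do not supply.

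**2. Chance difference in mean prior days**

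Standard error = s·√(2/n), with s = 5:

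- 100 per arm (the stated interim): 5·√(2/100) = 0.71 days
- 25 per arm (Section 1.0): 5·√(2/25) = 1.41 days

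This is the same noise as in step 1, not a further loss. At 100 per arm and r = 0, the variance of the difference in mean total stay is 2·89/100 = 1.78. For days after randomisation it is 2·64/100 = 1.28. The gap is 0.50 = 0.71².

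**3. Power** (two-sided 5%, normal outcome, assumed true difference 4 days, r = 0)

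| Prior-day SD | 25 per arm | 100 per arm | n per arm for 80% |
|---|---|---|---|
| 0 (count from Day 0) | 42.4% | 94.2% | 63 |
| 2 | 40.3% | 92.9% | 67 |
| 4 | 35.2% | 88.5% | 79 |
| 6 | 29.3% | 80.7% | 99 |

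**4. Bias or noise?** Both planned tests were simulated with skewed stays, with no treatment effect, and with mean prior ICU time of 0, 3 or 6 days. The type I error was 4.3% to 5.3% at 25 and 100 per arm. Randomisation balances prior days on average, so the comparison loses power but keeps its error rate.

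**The case against.** The strongest reply is that the plan is silent rather than wrong. It never says that the count starts at ICU admission. That is correct: a reader might infer that pre-trial days are certainly counted, but the text only leaves this open. The point is therefore stated as an undefined origin.

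Other stronger inferences also fail:

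- **That the result would be biased.** It would not. Prior days are fixed before randomisation, and their chance imbalance is already in the test's standard error.
- **That prior days could never be separated out.** Computing a total stay requires the ICU admission date, and the randomisation date is known, so prior days are one subtraction. A missing row in a visit schedule does not show that the date goes unrecorded. It shows only that the schedule does not ask for it.
- **That prior ICU time is long.** Its amount is unknown. The inclusion list in Section 5.2 largely repeats the ICU admission indications set out in Section 4.6, which fits entry near admission. Section 5.4 also describes an orotracheal or nasotracheal procedure in which the patient coughs, so some patients may not be intubated at entry.
- **That this is the leading endpoint.** Section 6 numbers its criteria without ranking them, and Section 5.5 makes death or a recovery composite primary.

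What remains is that three sections place patients in the ICU at entry, no rule limits prior days, and the usual meaning of the outcome would include them.

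**Conclusion.** The point holds as a cheap improvement. The time origin of ICU duration is undefined in a trial whose patients are described as already in the ICU. Under the ordinary reading, the planned comparison includes days that treatment cannot change. The consequence is generally lost precision, with no systematic error.

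Its size cannot be settled from the documents. Under the assumed SDs of 8 and 3 to 5 with zero correlation, variance rises 14% to 39%. A moderate negative correlation would remove the loss and a positive one would enlarge it. For the interim decision, the relevant chance imbalance at a prior-day SD of 5 is 0.71 days, at 100 per arm. The 1.4-day figure applies only if the trial is the 50-patient study of Section 1.0. If most patients are randomised within a day or so of ICU admission, the practical effect is small, but the definition is still needed.

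**What to change.** In Section 6, define criterion 1 as ICU days from randomisation (Day 0) to ICU discharge, counted identically in both arms. In the same place:

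- State when the count ends, and how deaths and patients still in the ICU after Day 15, the last scheduled visit, enter the test. Moving the origin alone is not enough: if death simply ends the count, an early death is scored as a short stay. One workable option is to fix the Mann-Whitney test and rank deaths as the worst outcome, with patients still in the ICU ranked after every discharge.
- Record the ICU admission and discharge dates for every patient.
- Report prior ICU days by arm as a baseline characteristic.

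The cost is one or two sentences in Section 6 and a few dates from the hospital chart. No procedure, visit or aspect of care changes.
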